3.1 General Design

This protocol is for a pilot study designed primarily to a) strengthen the evidence for using detailed clinical and electrophysiological characterization to predict the outcome and incidence of CIPN; b) obtain initial data evaluating the role of tissue oxygen as a potential biomarker for CIPN using EPR oximetry; and c) establish the feasibility of using EPR oximetry to correlate peripheral tissue oxygenation metrics with clinical and electrophysiological indices of CIPN. As a secondary objective, this pilot study will seek to demonstrate effective recruitment, screening, assessment, and retention in order to justify a larger trial in the future. The investigators will aim to enroll thirty (30) patients into the study over a one-year enrollment period. Subjects will have three study visits: Visit 1, before beginning chemotherapy treatment; Visit 2, mid-treatment; Visit 3, after completing chemotherapy. All subjects will undergo a neurologic evaluation and electrophysiological assessment in the form of nerve conduction studies and motor conductions at each study visit. Patients will have EPR tests at all study visits.

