4.4 Early Withdrawal of Subjects

4.4.1 When and How to Withdraw Subjects

Subjects will be withdrawn from the study if they are no longer able or willing to participate. If a participant is unable to continue with the study procedures or is deemed lost to follow up, the PI or designee will mail a signed letter to the patient to inform them of their withdrawal from the study. Subjects will be deemed lost to follow up if they fail to present for ongoing cycles of chemotherapy. If a subject declines additional cycles of chemotherapy or cannot complete the planned number of cycles, they will not be withdrawn, but a post chemo-therapy assessment will be performed. Subjects will be withdrawn if they develop an impairment that would interfere with clinical and electrophysiologic assessment.

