7.1 Sample Size Determination

This pilot study is designed for proof of concept and to establish the bedrock for a future trial with a more robust sample. The secondary objective of this pilot is to demonstrate effective recruitment, screening, assessment processes, and high participant retention. We will assess the proportion of potential participants that: meet inclusion criteria, consent to participate, and complete all assessments.

Thirty (30) patients will be enrolled in the study, and it has been estimated that ten (10) patients will develop CIPN during their taxane treatment. Accurate incidence of CIPN varies significantly; the average incidence is 70% (Seretny et al., 2014), with ranges from 30% to 90%. A conservative estimate is that 30%-50% of patients in this trial will develop symptoms of neuropathy during their chemotherapy treatment. Development of CIPN will be determined based on the results of their neurologic assessments. For data analysis, the patients will be divided by this CIPN status into two groups. Primary endpoints are continuous metrics: Endpoint 1) neurological phenotyping involves electrophysiological assessment (e.g. nerve conduction, EMG readings, SUDOSCAN results), and Endpoint 2) tissue oximetry involves the EPR measures). The mean levels of each electrophysiological or oximetry metric will be assessed between the two groups of patients (with CIPN vs. without) over time (at timepoints: before, mid-, and post-chemotherapy) using repeated measures ANOVA. This method will also assess the within-subject changes in the electrophysiological and EPR oximetry metrics over time, from baseline through post-chemotherapy, as well as the interaction between CIPN status and time. With 15 patients per group, we anticipate that we will have 80% power to detect a between-groups difference in longitudinal EPR oximetry measures by CIPN status of 28%, assuming a correlation of 0.5 among repeated measures, a standard deviation of 25%, alpha=0.05. The within-subjects and interaction tests are estimated to be able to detect an 8.5% change over time, with these same parameters (calculated using G*Power 3.1.9.2).

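### The repeated measures ANOVA in 7.1 has no rule for a missing timepoint, and in the worst case a Visit 3 EPR reading counted as post-chemotherapy can precede completion by up to 11 days

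*Combined protocol and SAP*

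**What the plan says.** **Analysis.** Section 7.1, the whole statistical plan, assesses each EPR and electrophysiological metric between the two CIPN groups "over time (at timepoints: before, mid-, and post-chemotherapy) using repeated measures ANOVA". It adds: "This method will also assess the within-subject changes", and it tests the interaction of CIPN status with time. Group membership is settled afterwards: "Development of CIPN will be determined based on the results of their neurologic assessments". There is no analysis set, imputation rule, mixed model or dropout allowance. Completeness appears only as a feasibility measure, the proportion who "meet inclusion criteria, consent to participate, and complete all assessments".

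**Who can be missing.** Section 4.4.1 withdraws patients who are unable or unwilling to continue or who develop an interfering impairment. It also has a loss-to-follow-up rule: "Subjects will be deemed lost to follow up if they fail to present for ongoing cycles of chemotherapy". Under 4.4.2, withdrawn patients have no further study assessments. In the other direction, 4.4.1 keeps early stoppers: "If a subject declines additional cycles of chemotherapy or cannot complete the planned number of cycles, they will not be withdrawn", and "a post chemo-therapy assessment will be performed".

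**Timing.** Section 3.1 places "Visit 3, after completing chemotherapy". Sections 6.1 and 6.4 put Visit 3 at least a week after chemotherapy ends. Both also allow up to five EPR readings within 18 days either side of the electrophysiologic assessment at that visit. No text limits the early side of this window to dates after completion.

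**The concern.** A three-timepoint repeated measures ANOVA in its usual form needs all three values from every patient. With 30 patients and about 10 expected CIPN cases, discarding a patient's two good timepoints because the third is absent wastes information. If the rule is left open, it may be chosen after the data are seen.

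The window raises a different problem. On-treatment readings can enter the level that 3.1 and 7.1 treat as post-chemotherapy, and so enter the within-subject change that 7.1 tests. Section 7.1 also gives, as an example of EPR utility, a 5% within-subject increase from baseline, so a shift of a few points in one level could matter to how the pilot is read.

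**Working it through.** **Inputs from 7.1:** 30 patients, about 10 expected to develop CIPN (so 10 and 20), SD 25%, correlation 0.5, alpha 0.05, three timepoints. **Assumed:** the numbers missing (the documents give none), equal correlation between visits, a two-sided test, and that the SD refers to one value per visit (7.1 does not say whether it is per reading or per visit mean).

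**The plan's own figure.** The SD of a patient's three-visit mean is 25 × √((1 + 2 × 0.5)/3) = 20.41. With 15 per group, the noncentral F test gives 80% power at a difference of 21.6%, and 95.2% power at 28%. The stated 28% at 80% power is therefore not reproduced. That is a separate matter, and nothing below depends on it.

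**Precision, complete cases.** SE = 20.41 × √(1/n₁ + 1/n₂), where n₁ and n₂ are the patients with all three visits.
- Full data: 20.41 × √(1/10 + 1/20) = 7.9
- 2 CIPN and 4 other patients lacking a visit: 20.41 × √(1/8 + 1/16) = 8.8

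**Precision, mixed model, CIPN status known.** Suppose a group has n patients, of whom m have the third visit. The best prediction of that visit from the other two has slope 0.5/1.5 = 1/3 on their sum and residual variance 625 × 0.5 × 2/1.5 = 416.7. The variance of the sum of the two observed visits is 2 × 625 × 1.5 = 1875. The variance of the group's three-visit mean is therefore

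(1/9) × [(4/3)² × 1875/n + 416.7/m] = 370.4/n + 46.3/m.

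For 2 and 4 missing: 37.04 + 5.79 + 18.52 + 2.89 = 64.24, so SE = 8.0.

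| Lacking one visit (CIPN, other) | Complete cases | Mixed model |
|---|---|---|
| 0, 0 | 7.9 | 7.9 |
| 1, 2 | 8.3 | 8.0 |
| 2, 4 | 8.8 | 8.0 |
| 3, 3 | 9.2 | 8.1 |

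**Detectable difference at 80% power, complete cases:** 22.9% at 10 and 20; 24.3% at 9 and 18; 25.9% at 8 and 16; 27.9% at 7 and 14. All are below 28%.

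**Bias and classification (simulation, assumed inputs).** CIPN means are 0, −10, −10 and the other group's are 0, so the true three-visit difference is −20/3 = −6.7. The odds of missing Visit 3 double per SD lower Visit 2 reading.

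| Missing Visit 3 (CIPN v other) | Complete cases | Mixed model, status known | Mixed model, half of CIPN leavers labelled no-CIPN |
|---|---|---|---|
| 30% v 15% | about −5.2 | about −6.7 | about −4.6 |
| 30% v 30% | about −6.6 | about −6.7 | about −4.6 |

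The mixed model's bias advantage therefore holds only while CIPN status is known. If leavers are classified by their last assessment, it can do worse than dropping them.

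**Window.** Take the last dose as completion (day 0); the documents do not define it.
- Visit 3 on day 7: window from 7 − 18 = −11 to 7 + 18 = +25, so 11 of 37 calendar days precede completion.
- Day 14: from −4 to +32, so 4 of 37.
- Day 18: from 0 to +36, so none.

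These are days on which a reading is permitted, not readings expected. As an illustration, suppose readings are averaged, 2 of 5 precede completion, and the on-treatment level differs by 10 points. That patient's post-chemotherapy mean then moves by 2/5 × 10 = 4 points.

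**The case against.** The strongest reply is that little is at stake. This is a proof-of-concept pilot. Section 4.4.1 keeps and assesses patients who decline or cannot complete cycles, which closes an obvious route to a missing Visit 3. The loss of precision is modest: 7.9 to 8.3 with three patients incomplete. The comparisons that 7.1 uses to prioritise early metrics are made within the pre- or mid-chemotherapy timepoint, so a missed Visit 3 removes nobody from them except through CIPN classification. All of this stands and limits the point. It does not supply an analysis rule: 4.4.1 governs data collection only.

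A second reply is that the obvious repair can do harm. The primary objective concerns patients who later develop CIPN. Classifying an early leaver by the last assessment puts those who would have developed it later in the wrong group. This also stands, and it shapes the fix.

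On the window, EPR is listed among the Visit 3 procedures, so the one-week minimum could be read as binding the readings too. That reading is possible, but the explicit two-sided 18 days is not limited in that way. The passages need reconciling.

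A reader might infer that the planned ANOVA biases the group difference. The documents do not support that. In the cases simulated, bias needs dropout that depends on EPR and also differs between groups, and no passage shows that dropout depends on EPR.

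**Conclusion.** The point holds as a cheap improvement, in two parts.

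1. Section 7.1 has no rule for a missing timepoint, and the conventional form of its ANOVA discards incomplete patients. On the assumed losses the cost is a standard error of 8.3 to 9.2, against 8.0 to 8.1 for a mixed model with CIPN status known. A reader might infer that dropout defeats the stated target. It does not: even with 7 and 14 complete patients the detectable difference is 27.9%, under the 28% stated.

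2. As written, a Visit 3 EPR reading can precede completion by up to 11 days. This is the worst case. It needs Visit 3 at its minimum and a reading at the early edge of the window, and it assumes that completion means the last dose. A reader might infer that post-chemotherapy readings are routinely taken on treatment; nothing in the documents says how often that would happen. Such readings can affect the within-subject change. They affect the group difference only if they are unequal between the groups.

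The precision gain applies to patients who lack an EPR timepoint but whose CIPN status is known. It does not recover patients who leave before any assessment after chemotherapy.

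**What to change.** **Missing timepoints.** In 7.1, replace the ANOVA with a linear mixed model (REML, small-sample degrees of freedom) with CIPN status, timepoint and their interaction. Include all EPR readings assigned to the three timepoints from every patient whose CIPN status is established by a neurologic assessment after chemotherapy, even if an EPR timepoint is missing. This includes the early stoppers kept in by 4.4.1. State that the model assumes missing at random. Do not classify early leavers by their last assessment in the primary analysis. Report them by reason and by visit, and include them only in sensitivity analyses that vary their classification.

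**Window.** Define completion. Count a reading at the post-chemotherapy level only if it is dated after completion, and report earlier readings in the Visit 3 window separately. A patient with no later reading is missing at that level and stays in through the other timepoints. Reconcile 3.1, 6.1, 6.4 and 7.1.

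**Cost.** A few sentences and one definition, with no new visits or data. The downside is slightly more modelling work and a few readings left out of the post-chemotherapy level.

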3.2 Primary Study Endpoints

The primary endpoint identified for the purposes of driving the sample size and primary analysis is: **the between-groups difference in longitudinal EPR oximetry measures by CIPN status.**

4 Subject Selection and Withdrawal

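### Section 7.1 pairs 80% power with a 28% between-groups EPR difference, but its own inputs give 80% power at 21.6% and about 95% power at 28%

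*Combined protocol and SAP*

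**What the plan says.** Section 3.2 names the between-groups difference in longitudinal EPR oximetry by CIPN status, introduced with "The primary endpoint identified for the purposes of driving the sample size and primary analysis is". Section 7.1 gives the analysis as a comparison of group means "over time (at timepoints: before, mid-, and post-chemotherapy) using repeated measures ANOVA".

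The power statement is also in Section 7.1. For 15 patients in each group it reads "we anticipate that we will have 80% power to detect a between-groups difference in longitudinal EPR oximetry measures by CIPN status of 28" per cent, "assuming a correlation of 0.5 among repeated measures, a standard deviation of 25%, alpha=0.05". The software is named as G*Power 3.1.9.2.

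Earlier in the same paragraph, of the 30 patients to be enrolled, "it has been estimated that ten (10) patients will develop CIPN during their taxane treatment". That is a 10 and 20 split, not 15 and 15.

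**The concern.** The power sentence supplies almost everything needed to repeat the calculation, and the timepoints stand a few lines above it. Repeating it does not return 28% at 80% power. This is the only power figure given for the between-groups comparison that Section 3.2 ties to the sample size, so the printed justification does not lead to the printed sample size. On these inputs, 28% at 80% power would need only about 10 per group.

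What is at stake is whether the plan's sensitivity is described correctly. A reader is told that the design reaches 80% power only at 28%, when on the stated inputs it does so at 21.6%.

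**Working it through.** **Inputs, all from Section 7.1.** Groups of 15 and 15 (N = 30); m = 3 timepoints; correlation ρ = 0.5; SD = 25 percentage points; alpha = 0.05. Sidedness is not stated; the ANOVA F test corresponds to a two-sided comparison. I take the SD to be the between-patient SD of a single measurement, which the text does not say.

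**Formula.** The between-groups test compares patient means over the m timepoints.

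- Variance of the difference: V = SD² × (1 + (m − 1)ρ)/m × (1/n₁ + 1/n₂)
- Noncentrality for a difference δ: λ = δ²/V, with F on 1 and N − 2 degrees of freedom

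For equal groups this is the usual G*Power form, λ = f²·N·m/(1 + (m − 1)ρ) with f = (δ/2)/SD.

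**Attempt to reproduce the plan's figure.**

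- V = 625 × (2/3) × (2/15) = 55.56, so SE = 7.45
- At δ = 28: λ = 784/55.56 = 14.11; the critical value of F(1, 28) is 4.196; power = 95.2%, not 80%

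**Detectable difference on the stated inputs.** 80% power needs λ = 8.42, so δ = 7.45 × √8.42 ≈ 21.6 (f = 0.433).

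| Power | Detectable difference |
|---|---|
| 80% | 21.6% |
| 90% | 25.0% |
| 95% | 27.8% |

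A normal approximation agrees closely: 20.9% at 80% power, and 96.4% power at 28%.

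**Can another reading give 28% at 80% power?**

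| Change to the inputs | 80%-power difference | Power at 28% |
|---|---|---|
| One timepoint, or ρ = 1 (15/15) | 26.5% | 84.1% |
| Two timepoints (15/15) | 22.9% | 92.8% |
| Five timepoints (15/15) | 20.5% | 96.9% |
| One-sided, three timepoints (15/15) | 19.0% | not computed |
| 10/20 split, three timepoints | 22.9% | 92.8% |
| 10/20 split, one timepoint (t-test) | 28.1% | 79.7% |

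For the 10/20 split with three timepoints, V = 625 × (2/3) × (1/10 + 1/20) = 62.5 and SE = 7.91, so δ = 7.91 × √8.42 ≈ 22.9.

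With 15 per group, SD 25% and alpha 0.05, the ceiling is 26.5%. Reaching 28% at 15/15 with three timepoints and ρ = 0.5 would take an SD of 25 × 28/21.63 = 32.4%. Keeping SD 25% and shrinking the groups, 10 per group gives 82.6% power at 28% and 9 per group gives 78.0%.

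**Dependence on the SD definition.** If 25% were instead a within-patient SD, then at ρ = 0.5 the single-measurement SD would be 25 × √2 = 35.4%. The 80%-power difference would be 30.6%, and power at 28% would be 73%. That does not return 28% at 80% power either, but it shows that 21.6% rests on the definition.

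**The case against.** **The error is harmless in direction.** On its stated inputs the design has more power than it claims, the study is a non-randomised proof-of-concept pilot, and the 28% appears only in this one sentence. No success threshold or stopping rule uses it; Section 7.1 ranks metrics by observed difference and p-value. All of this stands, and it lowers the severity. It does not make the sentence correct.

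**The cause is not known.** A reader might infer that G*Power was run at 95% power and the result labelled 80%. The documents do not support that. The 27.8% does round to 28%, but a single-timepoint t-test at the expected 10 and 20 split gives 28.1% at 80% power, which fits as well. The neighbouring 33% t-test difference does not settle it: with SD 25% it has 93.7% power at 15/15 and 90.8% at 10/20. If the t-test was the source, the sentence describes a different calculation from the one done.

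**The consequences can be overdrawn.** A reader might infer that a non-significant result would be taken to exclude only differences of 28% or more. No section says so, and exclusion is the work of a confidence interval, not of planned power. A reader might also infer that the next study would be about (27.84/21.63)² = 1.66 times too large. That assumes the same mislabelled set-up is reused, whereas Section 2 (Specific Aim 4) and Section 7.1 say the pilot's data will guide that study.

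**Correcting only the 15/15 figure would be incomplete.** This objection stands in full, because the same paragraph expects 10 patients with CIPN. The fix takes it in.

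**Conclusion.** The pairing of 28% with 80% power is wrong as written. On the stated inputs the 80%-power difference is 21.6%, so the printed value is 6.4 points, or about 29%, too high; power at 28% is 95.2%. At the plan's own expected split the figures are 22.9% and 92.8%.

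The result assumes three timepoints with equal correlation of 0.5, the two-sided F test, and 25% as the between-patient SD of one measurement. With 15 per group, that SD and alpha 0.05, no choice of timepoints or correlation rescues 28%.

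A reader might take a failed power calculation to mean that the study is underpowered. It does not show that: the error runs the other way, and nothing here says that 30 patients are too few. Severity: should fix.

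**What to change.** In Section 7.1:

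1. Restate the sentence: with 15 patients per group, 80% power for a between-groups difference of 21.6%, and 95% power for 28%.
2. Add the result for the expected split: with 10 patients with CIPN and 20 without, 80% power for 22.9%, and 92.8% power at 28%.
3. State that the 25% is the between-patient SD of a single measurement, and name three timepoints in the power sentence.
4. If 28% came from other inputs (a different SD definition, split or test), state those inputs instead and show that they match the planned analysis.

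The cost is a rerun of one calculation and a few sentences. Patients, procedures, sample size and analysis method do not change.

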We are particularly interested in identifying the metrics that allow the early identification of patients who go on to have a clinical diagnosis of CIPN. Within the pre- or mid-chemotherapy timepoints, the metrics that show a combination of the largest magnitude difference and lowest t-test p-value by CIPN status will be prioritized for future study. For primary endpoint 3), we will also use Pearson correlation to assess the relationship between metrics, for example, EPR oximetry will be assessed vs. a continuous CIPN metric (e.g. nerve conduction, temperature sensation, vibratory sensation) within a timepoint, e.g. post-chemotherapy). With n=30 patients, we anticipate having 80% power to detect at least a 33% difference in the means of a metric using an independent samples t-test comparing patients with CIPN vs. without, or a regression slope of 0.66 among continuous metrics, with a standard deviation of 0.25, and alpha of 0.05. This data will guide a larger study for which additional, external funding will be sought.

The potential utility of the EPR measures will be assessed in these CIPN patients using either a minimum within-subjects increase over time in the tissue oximetry measure of (e.g. 5%) compared to baseline, or a Pearson r threshold (e.g. -0.3) for the correlation between the tissue oximetry and electrophysiological measures of sensory or motor nerve conduction.

8 Safety and Adverse Events

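### Section 7.1 leaves its 8.5% detectable change undefined; read as a baseline-to-end change, its inputs give about 13–15% for time and 25–29% for the interaction

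*Combined protocol and SAP*

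**What the plan says.** Section 7.1 plans a repeated measures ANOVA of each metric by CIPN status over three timepoints (before, mid- and post-chemotherapy). It tests group, time and their interaction. The power statement begins "With 15 patients per group, we anticipate that we will have 80% power to detect a between-groups difference" in longitudinal EPR oximetry of 28%, "assuming a correlation of 0.5 among repeated measures, a standard deviation of 25%, alpha=0.05". The next sentence covers the other two tests: "The within-subjects and interaction tests are estimated to be able to detect an 8.5% change over time, with these same parameters". The software named is G*Power 3.1.9.2.

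The section does not give an effect size f, a pattern of visit means, or a definition of the 8.5%. It does describe the within-subject changes as running from baseline to post-chemotherapy. Earlier in the same section, "it has been estimated that ten (10) patients will develop CIPN during their taxane treatment", which implies about 10 vs 20 rather than 15 vs 15. On later use the plan says: "This data will guide a larger study for which additional, external funding will be sought".

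**The concern.** One percentage is given for two tests that measure different things. The time test concerns the average change across all 30 patients. The interaction concerns the difference between the CIPN and non-CIPN groups in that change. With 15 per group, the detectable difference in change is exactly twice the detectable average change, so a single figure for change over time cannot describe both.

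The figure also looks too small. It is about a third of the SD (8.5/25 = 0.34), which is demanding for 30 patients at correlation 0.5.

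The interaction asks whether oxygenation moves differently in patients who develop CIPN, which is close to the study's main question. If the pilot is believed able to see an 8.5-point difference, a null interaction could be taken to exclude modest differences that the pilot had little chance of finding. That belief could then carry into the larger study.

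**Working it through.** **Inputs, all from Section 7.1.** N = 30 (15 + 15), m = 3 visits, ρ = 0.5, SD = 25, α = 0.05, power 0.80. Assumed because not stated: sphericity and no dropout.

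**Required noncentrality.** Time and interaction both have df = 2 and 28 × 2 = 56. Solving the noncentral F(2, 56) for 80% power gives λ = 10.17.

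**Attempt to reproduce 8.5% on the G*Power scale.** With λ = N·m·f²/(1 − ρ):

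- f = √(10.17 × 0.5 / 90) = 0.238
- f × SD = 5.9%

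Both tests share this f, but neither f × SD nor 2f × SD (11.9%) equals 8.5%.

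**Conversion to a baseline-to-end change d.** λ = N_eff·Σ(dev²)/(SD²(1 − ρ)), where SD²(1 − ρ) = 625 × 0.5 = 312.5.

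- Step pattern (0, d, d): Σ(dev²) = 2d²/3
- Linear pattern (0, d/2, d): Σ(dev²) = d²/2
- Any monotone three-visit pattern falls between these two
- N_eff is 30 for time. For the interaction it is n₁n₂/(n₁ + n₂): 7.5 at 15 vs 15, or 6.67 at 10 vs 20
- d for the interaction is the between-group difference in change

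Examples: time, step, d = √(10.17 × 312.5 / (30 × 2/3)) = 12.6%. Interaction, 15 vs 15, linear, d = √(10.17 × 312.5 / (7.5 × 1/2)) = 29.1%.

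| Test | Detectable at 80% power (step to linear) | Power at 8.5% (step to linear) | ρ needed for 8.5% |
|---|---|---|---|
| Time, N = 30 | 12.6% to 14.6% | 0.45 to 0.35 | 0.77 to 0.83 |
| Interaction, 15 vs 15 | 25.2% to 29.1% | 0.14 to 0.12 | 0.94 to 0.96 |
| Interaction, 10 vs 20 | 26.7% to 30.9% | 0.13 to 0.11 | – |

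At 10 vs 20 with the groups weighted equally, the time range becomes 13.4–15.4%.

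**Ratios to the stated figure.** Time: 12.6/8.5 = 1.5 and 14.6/8.5 = 1.7. Interaction at 15 vs 15: 25.2/8.5 = 3.0 and 29.1/8.5 = 3.4.

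**Cross-checks.** A paired t test of baseline-to-end change (n = 30) detects 13.2%. A two-sample t test on change (15 vs 15) detects 26.5%. Both lie inside the ranges above. Simulation with 20,000 runs per case gave power of 0.797 to 0.806 at the detectable values in the table.

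**Other readings that come near 8.5%.**

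- Largest departure of a visit mean from the overall mean, step pattern: f × SD × √2 = 8.4%
- Correlation 0 instead of 0.5: f × SD = 8.4%
- Total N = 15 instead of 30: f × SD = 8.7%
- 8.5% per visit, means (0, 8.5, 17): power 0.91 for time but 0.35 for the interaction at 15 vs 15

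The first and last use an effect measure the plan does not state. The middle two change a stated input.

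**The neighbouring 28%.** The between-groups test has df = 1 and 28, and a subject mean has variance 625 × (1 + 2 × 0.5)/3 = 416.7. The stated inputs give a detectable difference of 21.6% (22.9% at 10 vs 20). Power at 28% is 0.95 (0.93). This figure also fails to reproduce, but it errs on the cautious side.

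**The case against.** The strongest reply is that the documents show an undefined figure, not a wrong one. One reading nearly works at the stated inputs: if 8.5% is the largest departure of a visit mean from the overall mean under a step pattern, the detectable value is 8.4%. It takes the same value for the interaction when applied to the group-by-visit cells, and power at 8.5% on that scale is 0.81 for both tests. That would explain why one number serves two tests. A second point is that the interaction factor of 3.0–3.4 treats 8.5% as the difference between groups in change. If the groups moved by equal amounts in opposite directions, each would move only 12.6–14.6%. Finally, the figure drives nothing: Section 3.2 names the between-groups difference as the endpoint behind the sample size, and the example utility thresholds in Section 7.1 do not use 8.5%.

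Part of this stands. The figure may be mislabelled rather than miscalculated, and only the authors can say which. But a departure from an overall mean is not what a change over time from baseline ordinarily means, and the plan states neither that measure nor the step pattern it needs. The opposite-directions case re-expresses the same 25–29% between-group difference. The limited consequence is accepted and is reflected in the verdict.

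**Conclusion.** The concern holds. The 8.5% is undefined, and on its natural reading as a baseline-to-end change the stated inputs do not deliver it, by the factors shown above for each test. The conclusion is conditional on that reading and assumes sphericity and no dropout; a sphericity correction or dropout would raise the detectable changes further. The origin of the 8.5% cannot be established from the documents. The point should be fixed as a matter of reporting: it changes neither enrolment nor any decision rule in this pilot, but it affects how a null interaction would be read.

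**What to change.** First, state what the 8.5% was meant to measure and give the G*Power entries: effect size f, total N, number of groups, number of measurements and correlation. If a different effect measure was intended, define it and state the assumed visit pattern.

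Otherwise, replace the sentence with separate figures, for example: *With the same inputs and 80% power, the time test can detect a baseline-to-end change of about 13% (step) to 15% (linear), and the interaction test a between-group difference in that change of about 25–29% at 15 vs 15, or 27–31% at 10 vs 20.*

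Recheck the 28% between-groups figure at the same time.

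The cost is wording in Section 7.1 only, with no extra patients, visits or measurements. The stated sensitivity for change over time becomes less favourable, and the between-groups figure may become more favourable.

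### Section 7.1: a 33% difference is not the 80%-power threshold for a t-test on 30 patients (it is 26.5% to 28.9%), and the slope of 0.66 cannot be checked without the predictor's SD

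*Combined protocol and SAP*

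**What the plan says.** Section 7.1 gives two sets of power figures. The first concerns the repeated-measures ANOVA and is not at issue here. The second concerns the comparisons at a single timepoint: t-tests by CIPN status, and the relations between continuous metrics that the section calls primary endpoint 3 and plans to analyse by Pearson correlation. For these it states, for n = 30: "we anticipate having 80% power to detect at least a 33% difference in the means of a metric using an independent samples t-test" between the two groups, "or a regression slope of 0.66 among continuous metrics, with a standard deviation of 0.25, and alpha of 0.05".

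No group split is given for this statement. Two appear earlier in the section. The repeated-measures calculation begins "With 15 patients per group, we anticipate that we will have 80% power to detect a between-groups difference in longitudinal EPR oximetry measures", while the accrual statement reads "Thirty (30) patients will be enrolled in the study, and it has been estimated that ten (10) patients will develop CIPN", which leaves 20 without. The section also expects 30% to 50% of patients to develop symptoms, so splits from 9/21 to 15/15. It does not say whether alpha is one- or two-sided, gives one SD without saying which variable it belongs to, and makes no allowance for dropout.

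**The concern.** With n, SD, alpha and power all fixed, the detectable difference in a t-test depends only on the split and the sidedness. The printed 33% looks too large for 30 patients with an SD of 0.25 under any split the section plans for. The slope of 0.66 is exactly twice 0.33, which suggests that the two figures come from one calculation and share one fault.

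These are the only stated sensitivities for the search for early metrics and for primary endpoint 3, and the section says the data will guide a larger study. A planner who works back from them would learn the wrong relation between sample size and detectable effect. The slope also hides the detectable correlation, which a reader needs when judging the section's own example utility threshold of r = -0.3.

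**Working it through.** **Inputs, all from section 7.1.** Total n = 30; SD 0.25; alpha 0.05 (taken as two-sided, an assumption); power 80%; splits 15/15 (repeated-measures calculation), 10/20 (ten expected cases) and 9/21 (30% incidence, the lower end of the expected range).

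**t-test.** The standard error of the difference is SE = 0.25 × √(1/n1 + 1/n2). The detectable difference is λ × SE, where λ is the noncentrality that gives 80% power in a two-sided noncentral t test with n1 + n2 − 2 degrees of freedom. For 28 df, λ = 2.902; for 18 df, λ = 2.963.

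| Split | SE | Detectable at 80% power | Power at 33% |
|---|---|---|---|
| 15/15 | 0.0913 | 2.902 × 0.0913 = 26.5% | 93.7% |
| 12/18 | 0.0932 | 2.902 × 0.0932 = 27.0% | 92.8% |
| 10/20 | 0.0968 | 2.902 × 0.0968 = 28.1% | 90.8% |
| 9/21 | 0.0996 | 2.902 × 0.0996 = 28.9% | 89.2% |
| 6/24 | 0.1141 | 2.902 × 0.1141 = 33.1% | 79.7% |
| 10/10 (n = 20) | 0.1118 | 2.963 × 0.1118 = 33.1% | 79.7% |

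The plan's 33% does not reproduce for any split in its 30% to 50% range. It does reproduce for 10 against 10, and for 30 patients split 6/24.

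**Other routes to 33% with 30 patients.** One-sided testing moves away from it (23% to 25% for 15/15 to 9/21). Alpha 0.01 with 15/15 gives 33.2%, and alpha 0.0167 with 10/20 gives 33.0%. Power of 90% gives 32.5% with 10/20 and 33.5% with 9/21. Each of these last routes contradicts the printed alpha or power.

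**Slope.** The noncentrality is slope × SDx × √n / SDresidual, with n − 2 df. If SDx and SDresidual are both 0.25 they cancel, and the detectable slope is λ/√n:

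- n = 30: 2.902/√30 = 0.530; power at 0.66 is 93.7%.
- n = 20: 2.963/√20 = 0.662; power at 0.66 is 79.7%.

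The link with the t-test is exact in this case. A balanced comparison has noncentrality d × √n / (2 × 0.25) and the slope has b × √n, so equal power means b = 2d. The printed pair, 0.33 and 0.66, satisfies this.

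The result depends on SDx. With residual SD 0.25 and n = 30, a slope of 0.66 is the 80% threshold if SDx = 2.902 × 0.25/(0.66 × √30) = 0.20. If instead 0.25 is the total SD of both variables, the slope equals the correlation and 30 patients detect 0.47; on that reading 0.66 would need only about 13 patients.

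**Correlation, the planned analysis.** By Fisher's z, the detectable r at n = 30 is tanh((1.960 + 0.842)/√27) = 0.49. The exact regression calculation above, with equal total SDs, gives 0.47.

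**The case against.** The strongest defence is that the statement is safe. Power for a 33% difference is at least 89% under every planned split, so a reader who trusts it is not misled into overrating the study. That stands. One might infer from a faulty power figure that the study is underpowered for the effects it names; the calculation shows the reverse. It is also true that no decision rule uses 33% or 0.66, that the t-tests only rank metrics for later study in a pilot, and that section 3.2 ties the sample size to the longitudinal EPR comparison, which has its own calculation.

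A reader might also infer that the figures were computed for 20 patients and mislabelled. The double match and the 2:1 ratio make that plausible, but the documents use no total of 20 for any analysis, and a 6/24 split of 30 gives the same 33.1%. That split means 20% CIPN, or 80% if the larger group is the affected one. Both lie outside the expected 30% to 50%, although 80% lies inside the wider 30% to 90% range that section 7.1 cites. The origin of the figure is therefore not established.

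Nor can the slope be called wrong outright. The section does not say whose SD is 0.25, and a predictor SD near 0.20 would make 0.66 correct for 30 patients.

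Finally, it would go too far to say that the design has 80% power across the whole range from 27% to 33%. At 27% the power is 77% with 10/20, and the claim holds only near 15/15.

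None of this rescues 33% as the 80%-power threshold for 30 patients at the planned splits.

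**Conclusion.** The t-test figure is wrong as written. With 30 patients, SD 0.25, two-sided alpha 0.05 and 80% power, the detectable difference is 26.5% to 28.9% across the planned range of splits, against the printed 33%. This rests on the section's own inputs plus two-sided testing; a one-sided test would widen the gap. The error is conservative.

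The slope of 0.66 is under-specified. It is too large (0.53 is the threshold) only on the unstated assumption that predictor and residual SD are both 0.25.

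An unlabelled calculation for 20 patients is a likely explanation, not a finding, and the documents do not show whether n, the split or the effects should change. Severity is minor to moderate: a stated sensitivity needs correcting, with no effect on the trial's conduct or on any decision rule.

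**What to change.** Replace the sentence in section 7.1 with, for example: *With n = 30, 80% power, SD 0.25 and two-sided alpha 0.05, the detectable difference in means is 26.5% (15/15) to 28.1% (10/20).* Give both splits, because the section uses both.

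Replace the slope with the detectable Pearson correlation at n = 30, about 0.47 to 0.49 depending on the method, which matches the planned analysis. Alternatively, keep a slope, give it as 0.53, and state that predictor and residual SD are both taken as 0.25.

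If the authors meant 20 evaluable patients, or a different split or SD, they should state that and keep the figures that follow from it. The cost is one corrected sentence, with no change to enrolment, visits or analysis.
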